6.3. Preparation/Handling/Storage/Accountability

6.3.1. Clinical Study Material Preparation

The study intervention will be prepared for each participant based on their vaccination group assignment. Details of the study interventions are provided in [Table 4](#). Specific instructions for the preparation of mRNA-1010 and active comparator are contained in the Pharmacy Manual.

6.3.2. Clinical Study Material Administration

mRNA-1010 or the active comparator will be administered as a single IM injection into the deltoid muscle in adult participants on Day 1. The study intervention should be administered preferably into the nondominant arm. The dose volume will be held constant at approximately **CC** mL per injection.

Participants will be monitored for at least 30 minutes after administration of the study intervention. Assessments will include vital sign measurements and monitoring for local or systemic reactions as shown in the SoE ([Table 1](#)).

The clinic will be appropriately staffed with individuals with basic cardiopulmonary resuscitation training/certification. Either onsite resuscitation equipment and personnel or appropriate protocols for the rapid transport of a participant to a resuscitation area or facility are required.

Further instructions for the preparation and administration of mRNA-1010 and active comparator are described in the Pharmacy Manual.

6.3.3. Clinical Study Material Packaging and Labeling

The Sponsor will provide the Investigator (via the clinic pharmacy) with adequate quantities of the study intervention. The study intervention will have all required labeling per regulations and will be supplied to the pharmacy in an unblinded manner.

All study interventions used in this study will be prepared, packaged, and labeled in accordance with the standard operating procedures of the Sponsor or those of its designee, Code of Federal Regulations (CFR) Title 21, GMP guidelines, International Council for Harmonisation (ICH) GCP guidelines, guidelines for Quality System Regulations, and applicable regulations.

6.3.4. Clinical Study Material Storage

mRNA-1010 must be stored at the clinical site at 2°C to 8°C in a secure area with limited access and must be protected from moisture and light until it is prepared for administration. The refrigerator should have automated temperature recording and a 24-hour alert system in place that allows for rapid response in case of refrigerator malfunction. The refrigerator should be connected to a backup generator. In addition, for study intervention accountability, site staff are required to keep a temperature log to establish a record of compliance with these storage conditions. The clinic is responsible for reporting any study intervention that was not temperature controlled during shipment or storage. Such study intervention will be retained for inspection by the monitor and disposed of according to approved methods. mRNA-1010 will be stored at -25°C to -15°C at the depots and during shipments to the clinical sites.

The active comparator should be stored in its original container and in accordance with the instructions in the Pharmacy Manual.

6.3.5. Clinical Study Material Accountability

The Investigator is responsible for ensuring the study intervention accountability staff maintain an accurate record of the shipment receipt, the inventory at the site, dispensing of study intervention, and the return to the Sponsor or alternative disposition of used/unused product(s) in a drug accountability log. Drug accountability will be noted by the site monitor during site visits and at the completion of the study. For further direction, refer to the Pharmacy Manual.

6.3.6. Clinical Study Material Handling and Disposal

A site monitor will reconcile the clinical study material during study conduct and at the end of the study for compliance. Once fully reconciled at the site, the clinical study material can be destroyed at the investigational site or a Sponsor-selected third party, as appropriate.

Clinical study material may be destroyed at the clinic only if permitted by local regulations and authorized by the Sponsor. A Certificate of Destruction must be obtained and sent to the Sponsor or designee. For further direction, refer to the Pharmacy Manual.

6.3.7. Unblinding

Except in the case of medical emergency, a participant's treatment assignment should not be unblinded without the approval of the Sponsor. If a participant becomes seriously ill or pregnant during the study, the blind will be broken only if knowledge of the treatment assignment will affect that participant's clinical management (see [Section 11.6](#) for country-specific amendment

affecting this paragraph). In the event of a medical emergency requiring identification of individual treatment assignment, the Investigator must promptly contact the CRO clinical research associate to explain the need for unblinding within 24 hours of opening the code. The Investigator will be responsible for documenting the time, date, reason for unblinding, and the names of the personnel involved. The Investigator (or designee) will have access to unblind participants within IRT. All unblinding will be tracked via an audit trail in IRT and documented in the final study report.

6.4. Study Intervention Compliance

All study interventions will be administered by qualified and trained study personnel to ensure that all doses administered comply with those planned. Study vaccine administration will be recorded in the eCRF. Administration data will be reconciled with site accountability records to determine compliance.

6.5. Concomitant Therapy

At each visit, the site personnel should question the participant regarding any medications taken and vaccinations received and record the information as specified in [Section 6.5.1](#).

6.5.1. Recording of Concomitant Medications and Concomitant Vaccinations

The following concomitant medications and vaccines must be recorded in the eCRF:

- All non-study vaccinations administered within the period starting 28 days before the study intervention and through Day 361/EoS.
- All concomitant medications taken through 28 days after the study intervention. Antipyretics and analgesics taken prophylactically (ie, taken in the absence of any symptoms in anticipation of an injection reaction) will be recorded as such.
- Any authorized or investigational COVID-19 vaccine at any time before the study intervention.
- Any authorized influenza vaccine administered since August 2021.
- Systemic steroids (≥ 10 mg/day prednisone or equivalent), immunosuppressants, immunoglobulins and long-acting biological therapies that affect immune responses (eg infliximab), and/or blood products administered at any time during the study period after the study intervention.
- Any concomitant medications relevant to or for the treatment of an SAE, AESI, or medically attended AE (MAAE) from Day 1 through Day 361 (Month 12)/EoS.
- The participant will be asked to record in the eDiary if they have taken any antipyretic or analgesic to treat or prevent fever or pain within 7 days after the study intervention, including the day of injection. Reported antipyretic or analgesic medications should be recorded in the source document by the clinic staff during the clinic visits after vaccination or via other participant interactions (eg, telephone calls).

Concomitant medications (including vaccinations) will be coded using the WHO Drug Global.

It is the Investigator's responsibility to ensure that details regarding the concomitant medications are adequately recorded in the eCRF.

6.5.2. Concomitant Medications and Vaccines that May Lead to the Elimination of a Participant from Per-Protocol Analyses

The use of the following concomitant medications and/or vaccines will not require withdrawal of the participant from the study but may determine a participant's evaluability in the Per-protocol (PP) Set. Analysis sets are described in [Section 9.4](#).

- Any investigational or nonregistered product (drug or vaccine) other than the study intervention used during the study period.
- Immunosuppressants administered chronically (ie, more than 14 days in total) during the study period. For glucocorticosteroids, this will mean that prednisone ≥ 10 mg/day or the equivalent is not permitted. Inhaled, nasal, intra-articular, and topical steroids are allowed.
- An authorized or licensed noninfluenza vaccine that is not adjuvanted administered within 14 days before or after the study intervention.
- An authorized or licensed adjuvanted, noninfluenza vaccine administered within 28 days after the study intervention.
- Any non-study influenza vaccine administered during the study period.
- Immunoglobulins and long-acting biological therapies that affect immune responses (eg, infliximab) and/or any blood products administered during the study period.

6.6. Continuous Access to Study Intervention After the End of the Study

There will be no access to study intervention following the end of the study.

7. DELAY OR DISCONTINUATION OF STUDY INTERVENTION AND PARTICIPANT DISCONTINUATION/WITHDRAWAL

7.1. Participant Discontinuation/Withdrawal from the Study

Participants who withdraw or are withdrawn from the study will not be replaced. From an analysis perspective, a “withdrawal” from the study refers to a situation wherein a participant does not return for the final visit foreseen in the protocol.

Participants can withdraw consent and withdraw from the study at any time, for any reason, without prejudice to further treatment the participant may need to receive. The Investigator will request that the participant complete all study procedures pending at the time of withdrawal.

If a participant desires to withdraw from the study because of an AE, the Investigator will attempt to obtain agreement to follow-up with the participant until the event is considered resolved or stable and will then complete the EoS section of the eCRF.

All data collected until the date of withdrawal or last contact of the participant will be used for the analysis.

Information relative to the withdrawal will be documented in the eCRF. The Investigator will document whether the decision to withdraw a participant from the study was made by the participant, or by the Investigator, as well as which of the following possible reasons was responsible for withdrawal:

- AE (specify)
- SAE (specify)
- Solicited AR or reactogenicity event (specify)
- Death
- Lost to follow-up
- Physician decision (specify)
- Pregnancy
- Protocol violation
- Study terminated by Sponsor
- Withdrawal of consent by participant (specify)
- Other (specify)

Participants who are withdrawn from the study because of AEs (including SAEs or solicited ARs) must be clearly distinguished from participants who are withdrawn for other reasons. Investigators will follow-up with participants who are withdrawn from the study as a result of an AE, SAE, or solicited AR until resolution or stabilization of the event.

If a participant withdraws from the study, they may request destruction of any samples taken and not tested, and the Investigator must document this in the site study records.

If the participant withdraws consent for disclosure of future information, the Sponsor may retain and continue to use any data collected before such a withdrawal of consent (see [Section 11.1.6](#)).

The Sponsor will continue to retain and use all research results that have already been collected for the study evaluation. All biological samples that have already been collected may be retained and analyzed at a later date (or as permitted by local regulations).

7.2. Lost to Follow up

A participant will be considered Lost to Follow-up (LTFU) if the participant repeatedly fails to return for scheduled visits without stating an intention to withdraw consent and is unable to be contacted by the study site. The following actions must be taken if a participant fails to return to the clinic for a required study visit:

- The site must attempt to contact the participant and reschedule the missed visit as soon as possible, counsel the participant on the importance of maintaining the assigned visit schedule and ascertain whether the participant wishes to and/or should continue in the study.
- Before a participant is deemed lost to follow up, the Investigator or designee must make an effort to regain contact with the participant (where possible, 3 telephone calls and, if necessary, a certified letter to the participant's last known mailing address or locally equivalent methods). These contact attempts (eg, dates of telephone calls and registered letters) should be documented in the participant's medical record.
- Should the participant continue to be unreachable, the participant will be considered to have withdrawn from the study.
- A participant should not be considered LTFU until due diligence, as described above, has been completed.

8. STUDY ASSESSMENTS AND PROCEDURES

The study SoE can be found in [Table 1](#).

Before performing any study procedures, all participants will sign an informed consent form (ICF [Section 11.1.6](#)).

8.1. Screening

At the Screening visit (up to 28 days before the Day 1 visit), all screening requirements, including the Screening Status eCRF to indicate if a participant is either a screen failure or not, must be completed.

The Screening visit and Day 1 visit may be performed on the same day or a different day. Additionally, the Screening visit may be performed over multiple visits if within the 28-day screening window.

8.2. Confirm Inclusion and Exclusion Criteria

All inclusion and exclusion criteria described in [Section 5.1](#) and [Section 5.2](#) must be met before randomization (Day 1 visit).

8.3. Demographic and Baseline Data

Demographic information relating to the participant's sex, age, ethnicity, and race will be recorded at Screening on the appropriate eCRF page.

8.4. Medical History

Medical history (including verbal history) from each participant will be collected and recorded on the appropriate eCRF page. Significant findings that were present prior to study vaccination must be included in the Medical History eCRF page.

8.5. Randomization

Study intervention group and study intervention assignment allocation will be performed on Vaccination Visit (Day 1) as described in [Section 6.2](#). The confirmation for study vaccine administration must be recorded on the Injection eCRF page.

8.6. Physical Examination and Vital Signs

A full physical examination will be performed at the Screening visit (according to standard medical practice, including assessment of height and weight). Vital sign measurements must include the assessment of body temperature (oral being the preferred route), systolic and diastolic blood pressures, heart rate, and respiratory rate. The information collected will be recorded in the eCRF.

Vital signs will be measured by study site staff at the Day 1 visit prior to vaccination and approximately 30 minutes after vaccination, prior to discharge of the participant.

Symptom-directed physical examinations will be performed at all other scheduled timepoints as specified in the SoE (Table 1). Interim physical examinations may be performed at the discretion of the Investigator.

Vital signs may be collected at other clinic visits in conjunction with a symptom-directed physical examination.

Treatment of any abnormality observed during physical examination should be performed according to local medical practice outside the study or by referral to an appropriate healthcare provider at the discretion of the Investigator.

8.7. Study Vaccine Administration

A single dose vaccination (mRNA-1010 or active comparator) will be administered to all participants.

After completing all prerequisite procedures prior to vaccination, the study intervention will be administered via a single IM injection into the deltoid muscle. A detailed description of the vaccine administration procedure is provided in Section 6.3.2.

The participants will be observed closely (via clinical assessment including measurement of vital signs) for at least 30 minutes following administration of the study intervention, with appropriate medical treatment readily available in case of anaphylaxis or other hypersensitivity reactions.

8.8. Efficacy Assessments

Assessment will be conducted to document RT-PCR-confirmed protocol-defined-ILI that begins at least 14 days post vaccination through Day 181 (Month 6)/end of influenza season caused by any influenza A or B virus strains or by strains similar to or antigenically matched to the strains selected for the seasonal vaccine.

Participants who develop symptoms consistent with protocol-defined ILI will have NP swabs collected for testing and ILI symptoms assessed. The initial test on the NP swab will be a real-time RT-PCR-based assay, to determine if either influenza A and/or B strains, as well as other respiratory viruses such as SARS-CoV-2, are present in the clinical sample. For samples that test positive for influenza in the RT-PCR assay, additional assays such as genetic sequencing of the virus genes and/or virus culture with subsequent antigenicity testing will be performed to determine vaccine match or similarity.

8.9. Safety Assessments

Safety assessments will include monitoring and recording of the following for each participant in the study:

- Solicited local and systemic ARs (Section 8.10.3) that occur through the 7 days following the study intervention (ie, the day of injection and 6 subsequent days). Solicited ARs will be recorded daily using eDiary (Section 8.9.4).
- Unsolicited AEs (Section 8.10.1) observed or reported through the 28 days following the study intervention (ie, the day of injection and 27 subsequent days). Unsolicited AEs are defined in Section 8.10.1.

- AEs leading to discontinuation from study participation from Day 1 through Day 361 (Month 12)/EoS or withdrawal from the study.
- MAAEs from Day 1 through Day 361 (Month 12)/EoS or withdrawal from the study. MAAEs are defined in [Section 8.10.4](#).
- AESIs from Day 1 through Day 361 (Month 12)/EoS or withdrawal from the study. AESIs are defined in [Section 8.10.6](#).
- SAEs from Day 1 through Day 361 (Month 12)/EoS or withdrawal from the study. SAEs are defined in [Section 8.10.2](#).
- Vital signs measurement.
- Details of all pregnancies in female participants will be collected after the start of study intervention and until the end of their participation in the study ([Section 8.9.5](#)). All pregnancies must be followed to determine the outcome; however, pregnancy related-data received after the end of the study may not be collected in the clinical database.

Planned time points for all safety assessments are provided in the SoE ([Table 1](#)).

8.9.1. Pregnancy Screen and Testing

A pregnancy test via point of care urine test will be performed for all female participants of childbearing potential at the Screening visit and before the vaccine dose on Day 1, if Day 1 is not on the same day as the Screening visit. At the discretion of the Investigator, a pregnancy test either via blood or point-of-care urine can be performed at any time. Additional pregnancy testing during the study may also be performed if required by local regulatory requirements. The participant's FSH level may be measured at the Screening visit, as necessary, and at the discretion of the Investigator, to confirm postmenopausal status ([Section 11.2](#)).

Further details on reporting and follow-up of pregnancy are provided in [Section 8.9.5](#).

8.9.2. Assessments for Respiratory Viral Infections

The NP swab specimen(s) for pathogens, including influenza virus, will be collected any time from Day 1 to Day 361 (Month 12)/EoS if participants have protocol-defined ILI ([Section 8.10.5](#)) or if deemed necessary per Investigator's discretion when influenza is suspected. If participants experience these signs or symptoms, they will be instructed to contact the clinic to determine if they need an NP swab collected for testing. NP swab collection should occur within 72 hours of symptom onset. Sites may follow up with participants for symptom review if illness symptoms are noted upon review of the Symptom Reporting eDiary to assess whether the participant is required to provide an NP swab. NP swab should be collected prior to any antiviral therapy, if possible. NP swabs may be collected as part of a home visit in lieu of a clinic visit. In the event that NP swabs during ILI cannot be collected, any available influenza testing results performed outside of the study should be captured in the eCRF.

Participants who experience protocol-defined ILI ([Section 8.10.5](#)) must have NP swabs collected for RT-PCR testing of influenza virus and other respiratory pathogens. For participants who experience ILI symptoms but have not yet fulfilled protocol-defined ILI definition, Investigators may use their discretion to perform NP swabs when influenza is suspected. If Investigator

discretion is applied, participant should be followed-up for any new symptoms following NP swab collection.

Symptoms reporting for ILI will be conducted between Day 1 through Day 361 (Month 12)/EoS as described in [Section 8.9.4](#).

All cases that meet the definition of RT-PCR-confirmed influenza infection should be captured as MAAEs along with relevant concomitant medications, hospitalizations, outpatient medical care, and details about severity, seriousness, and outcome.

If an unscheduled visit for assessment of protocol-defined ILI occurs within the first 28 days post study injection, the event should be captured as an unsolicited AE on the Adverse Event eCRF page. If such an unscheduled visit occurs after Day 29, it should be captured as an AE only if it meets MAAE definition (additional medical evaluation, including examinations/testing not required per protocol, and/or treatment is provided during the visit) **OR** if the participant meets RT-PCR confirmed influenza infection (RT-PCR with positive result for influenza) ([Section 8.10.5](#)).

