
 To evaluate the safety and reactogenicity of mRNA-1010 during the treatment period (28 days after study intervention) and follow-up period (period following the treatment period). 	
 Solicited local and systemic ARs through 7 days after study injection. Unsolicited AEs through 28 days after study injection.

	
 • MAAEs from Day 1 to Day 361 (Month 12)/EoS. • AESIs from Day 1 to Day 361 (Month 12)/EoS. • SAEs from Day 1 to Day 361 (Month 12)/EoS. • AEs leading to discontinuation from Day 1 to Day 361 (Month 12)/EoS.

 • To evaluate relative vaccine efficacy of mRNA-1010 as compared to an active comparator against influenza caused by any influenza A or B virus strains using protocol-defined ILI definition. 	
 • First episode of RT-PCR confirmed protocol-defined ILI that begins at least 14 days post vaccination through Day 181 (Month 6)/end of influenza season caused by any seasonal influenza A or B virus strains regardless of antigenic match to strains selected for the seasonal vaccine.
Secondary Objectives	Secondary Endpoints

 • To evaluate relative vaccine efficacy of mRNA-1010 vaccine as compared to an active comparator against influenza caused by influenza A or B strains with similarity^a to the vaccine strains using protocol-defined ILI definition. 	
 • First episode of RT-PCR confirmed protocol-defined ILI that begins at least 14 days post vaccination through Day 181 (Month 6)/end of influenza season caused by influenza A or B strains with similarity^a to those selected for the seasonal vaccine.

 • To evaluate relative vaccine efficacy of mRNA-1010 vaccine as compared to an active comparator against influenza caused by influenza A or B strains antigenically matched to the vaccine strains^b using protocol-defined ILI definition. 	
 • First episode of RT-PCR confirmed protocol-defined ILI that begins at least 14 days after vaccination through Day 181 (Month 6)/end of influenza season caused by influenza A or B strains antigenically matched to the vaccine strains^b selected for the seasonal vaccine.

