8.10.4. Medically Attended Adverse Events

An MAAE is an AE that leads to an unscheduled visit to an HCP. This would include visits to a study clinic for unscheduled assessments (eg, rash assessment, abnormal laboratory follow-up) and visits to HCPs external to the study clinic (eg, emergency room, urgent care, primary care physician). Investigators will review unsolicited AEs for the occurrence of any MAAEs. Unsolicited AEs will be captured on the AE page of the eCRF.

An unscheduled visit for assessment of protocol-defined ILI (symptoms assessment and NP swab) is not considered an MAAE unless additional medical evaluation, including examinations/testing not required per protocol, and/or treatment is provided during the visit, **OR** if the participant meets RT-PCR confirmed influenza infection (RT-PCR with positive result for influenza) ([Section 8.10.5](#)).

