9.5.2.1. Adverse Events

Safety and reactogenicity will be assessed by clinical review of all relevant parameters, including solicited ARs (local and systemic events), unsolicited AEs, SAEs, MAAEs, AESIs, AEs leading to discontinuation, vital signs, and physical examination findings.

Unsolicited AEs will be coded by system organ class and preferred term according to the MedDRA terminology. The Toxicity Grading Scale for Healthy Adult and Adolescent Volunteers Enrolled in Preventive Vaccine Clinical Trials ([DHHS 2007](#)) will be used in this study.

The number and percentage of participants with any solicited local AR, solicited systemic AR, and any solicited AR during the 7-day follow-up period after the study intervention will be summarized. A 2-sided 95% exact CI using the Clopper-Pearson method will also be provided for the percentage of participants with any solicited AR for each vaccination group.

Number and percentage of participants with unsolicited AEs, SAEs, MAAEs, AESIs, severe AEs, and AEs leading to discontinuation from the study will be summarized. Numbers of events of unsolicited AEs, SAEs, MAAEs, and AESIs will be reported in summary tables accordingly.

For all other safety parameters, descriptive summary statistics will be provided, and [Table 7](#) summarizes analysis strategy for safety parameters. Further details will be described in the SAP.

Table 7: Analysis Strategy for Safety Parameters

Safety Endpoint	Number and Percentage of Participants, Number of Events	95% CI
Any Solicited AR (overall and by local, systemic)	X	X
Any Unsolicited AE	X	
Any SAE	X	
Any AESI	X	
Any Unsolicited MAAE	X	
Any Unsolicited Treatment-Related AE	X	
Any Treatment-Related SAE	X	
Discontinuation due to AE	X	
Any Grade 3 and above AE	X	
Any Treatment-Related Grade 3 and above AE	X	

Abbreviations: AE = adverse event; AESI = adverse event of special interest; AR = adverse reaction; CI = confidence interval; MAAE = medically-attended adverse event; MedDRA = Medical Dictionary for Regulatory Activities; SAE = serious adverse event.

Notes: 95% CI using the Clopper-Pearson method, X = results will be provided. Unsolicited AEs will be summarized by system organ class and preferred term coded by MedDRA.

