6.7.1.1. Overview of Unsolicited TEAEs

An overall summary of unsolicited TEAEs occurring up to 28 days after IP injection including the number and percentage of participants, along with the number of events, by vaccination group who experience the following will be presented:

- Any unsolicited TEAEs
- Any unsolicited treatment-related TEAEs
- Any serious TEAEs
- Any treatment-related serious TEAEs
- Any unsolicited severe TEAEs
- Any unsolicited treatment-related severe TEAEs
- Any unsolicited treatment-emergent MAAEs
- Any unsolicited treatment-related treatment-emergent MAAEs

- Any unsolicited treatment emergent AESIs
- Any unsolicited TEAEs leading to discontinuation from participation in the study
- Any unsolicited TEAEs that are fatal

In addition, separate listings containing individual participant AE data for unsolicited AEs, unsolicited serious AEs, unsolicited severe AEs, unsolicited MAAEs, unsolicited AESIs as assessed by investigator, unsolicited AEs leading to discontinuation from participation in the study, and unsolicited adverse events leading to death will be produced. A separate listing of deaths will also include the cause of death.

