6.7.1.2. TEAEs by System Organ Class and Preferred Term

The following summary tables of TEAEs occurring up to 28 days after IP injection will be provided by SOC and PT using frequency counts and percentages (i.e., number and percentage of participants with an event) and number of events:

- Any unsolicited TEAEs
- Any unsolicited treatment-related TEAEs
- Any serious TEAEs
- Any treatment-related serious TEAEs
- Any unsolicited severe TEAEs
- Any unsolicited treatment-related severe TEAEs
- Any unsolicited treatment-emergent MAAEs
- Any unsolicited treatment-related treatment-emergent MAAEs
- Any unsolicited treatment emergent AESIs
- Any unsolicited TEAEs leading to discontinuation from participation in the study.

Unsolicited TEAEs and unsolicited treatment-related TEAEs will be summarized by SOC and PT for TEAEs with occurrence in $\geq 1\%$ of participants in any vaccination group based

on PT and presented by SOC and PT and maximum severity using frequency counts and percentages.

Summary tables for all unsolicited SAEs, AESIs, MAAEs, AEs leading to discontinuation from the study, and AEs leading to death occurring throughout the study (up to Day 361 (Month 12)/EoS) will be provided by SOC and PT as applicable.

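### The whole-study any-MAAE total counts every RT-PCR confirmed influenza case, so it carries the efficacy effect; one added row without influenza would separate the two

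*Protocol*

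**What the plan says.** Protocol 8.9.2 sets the counting rule: "All cases that meet the definition of RT-PCR-confirmed influenza infection should be captured as MAAEs". Protocol 8.10.4 gives the same rule from the other side. A visit made only for the ILI symptom check and swab is not an MAAE unless further evaluation or treatment is given, or "if the participant meets RT-PCR confirmed influenza infection". Protocol 8.9.2 adds that after Day 29 such a visit is recorded as an AE only if one of those two conditions is met.

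The primary safety endpoints include "MAAEs from Day 1 to Day 361 (Month 12)/EoS" (Protocol 1.1, repeated in Protocol 3 and SAP 3.1.1). Three outputs use MAAEs:

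- Protocol Table 7 (9.5.2.1) has a row "Any Unsolicited MAAE", with counts and percentages but no confidence interval.
- The SAP overview of unsolicited TEAEs (6.7.1.1) has a row "Any unsolicited treatment-emergent MAAEs", limited to 28 days after injection.
- For the whole study, SAP 6.7.1.2 plans "Summary tables for all unsolicited SAEs, AESIs, MAAEs, AEs leading to discontinuation from the study" and deaths, which "will be provided by SOC and PT as applicable".

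Neither document plans an MAAE summary that leaves out influenza cases.

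**The concern.** Two participants can have the same symptoms, the same protocol-required visit and no extra care. One has an MAAE and the other does not, and the only difference is the influenza result. MAAE status therefore depends partly on the primary efficacy outcome.

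If mRNA-1010 prevents more influenza than the comparator, its MAAE total falls for that reason alone. A modest excess of other medically attended events, spread over many terms, could then leave the two totals looking alike. If mRNA-1010 prevents less influenza, the total shows an excess that reflects efficacy and not harm. In both cases a reader of the total cannot tell the two sources apart.

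**Working it through.** **Inputs from the plan** (Protocol 9.3, SAP 4.3): 11,500 participants per arm; comparator attack rate 2%; target rVE 25%, so 1.5% on mRNA-1010; 4% not evaluable for the mITT Set.

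**Reproducing the plan's case count.** 11,500 × 0.96 × (0.020 + 0.015) = 386.4, against 386 stated.

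**Influenza cases that become MAAEs, by arm**

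- Comparator: 11,500 × 0.96 × 0.020 = 220.8
- mRNA-1010: 11,500 × 0.96 × 0.015 = 165.6
- Difference: 55.2 participants; 55.2 / 11,500 = 0.48 points

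If the 4% also contribute cases, the difference is 11,500 × 0.005 = 57.5 participants, or 0.50 points.

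**Allowing for overlap.** A participant with influenza and another MAAE is already in the total. Let *b* be the proportion with another MAAE, independent of influenza. The shift in the any-MAAE total is then 0.48 × (1 − *b*). The standard error of the arm difference is approximately √(2*b*(1 − *b*)/11,500). The documents give no *b*; 10% to 40% over 12 months is an assumption.

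| *b* | Shift (points) | SE (points) | Shift / SE |
|---|---|---|---|
| 10% | 0.43 | 0.40 | 1.1 |
| 20% | 0.38 | 0.53 | 0.7 |
| 30% | 0.34 | 0.60 | 0.6 |
| 40% | 0.29 | 0.65 | 0.45 |

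The standard error serves only as a yardstick, since no test is planned.

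**Excess of other MAAEs that would be cancelled.** Let the mRNA-1010 proportion with other MAAEs be *b′*. On the randomized denominators the influenza proportions are 1.92% and 1.44%. The totals are equal when (1 − *b′*) × 0.9856 = (1 − *b*) × 0.9808, which gives *b′* − *b* = (1 − *b*) × 0.0048 / 0.9856. This is 0.44 points at *b* = 10% and 0.29 points at *b* = 40%, about the same as the shift.

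**Direction.** At rVE −10% the case difference is 220.8 × 0.10 = 22 participants (0.19 points) the other way, before overlap.

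**The 28-day overview.** Assume cases are uniform over 181 days and the full effect acts from Day 1. Then 11,500 × 0.02 × (28/181) × 0.25 = 8.9 participants, or 0.08 points.

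**The case against.** Most of the case on the other side concerns scope, and it stands.

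- **No MAAE comparison is formally tested.** Reporting is descriptive, and Protocol 9.5.2.1 and SAP 6.7 assess safety by clinical review. No decision rule is wrong. Clinical review does, however, look at arm totals.
- **The SAP overview covers 28 days**, which SAP 6.1.7 makes the primary period for unsolicited safety data. The shift there is about 9 participants. The concern belongs to the whole-study summary only.
- **Influenza has its own preferred-term row**, and treatment-related MAAEs, SAEs, severe TEAEs and AESIs are tabulated separately. A signal in a particular term would still be seen on its own row. What could be hidden is a thin excess across many terms.
- **SAP 6.7.1.1 plans participant-level listings of MAAEs**, from which the count without influenza could be worked out. The preferred-term rows cannot give it, because a participant may appear on several. A listing makes the count possible but does not plan it.
- **Some influenza cases would be MAAEs anyway**, through extra evaluation or treatment. As a measure of what the counting rule adds, 0.48 points is therefore an upper bound. Those cases carry the efficacy effect too, so removing only events that qualify solely by the swab result would leave part of it in the total.

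A reader might infer that the plan's MAAE safety assessment as a whole is biased, or that the overview table would conceal harm. The documents do not support either reading, for the first three reasons above.

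**Conclusion.** The point holds for the any-MAAE participant total over Day 1 to Day 361. At the planning assumptions it contains an efficacy difference of up to about 55 participants (0.48 points) in favour of mRNA-1010. After overlap this is about 0.43 points (1.1 SE) at an assumed 10% with other MAAEs and 0.29 points (0.45 SE) at 40%. A diffuse excess of other MAAEs of about that size could go unseen in the total.

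The size rests on the plan's attack rate and rVE, an assumed range for other MAAEs, and independence of the two. It scales with the attack rate: on all 11,500 per arm and before overlap, 0.25 points at 1% and 1.0 point at 4%. The 2% refers to cases from 14 days after vaccination to Day 181 or the end of the season, while MAAEs run to Day 361.

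The table shells are not in the documents. That the whole-study table opens with an any-MAAE line is therefore inferred from the endpoint, Protocol Table 7 and SAP 6.1.7. This is a cheap improvement to reporting and not a fault in any planned test.

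**What to change.** In the whole-study MAAE summary (SAP 6.7.1.2, TEAEs by System Organ Class and Preferred Term), add the number and percentage of participants with any MAAE excluding all RT-PCR confirmed influenza events, Day 1 to Day 361. Show it beside the all-inclusive count, with the between-group difference and 95% CI. Exclude every RT-PCR confirmed influenza event, not only those that qualify solely by the swab; this also avoids having to establish why each event qualified.

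The 28-day overview can stay as it is. SAP 6.3.1.1 already derives RT-PCR confirmed protocol-defined ILI cases with start dates, so the work is one flag linking those cases to the AE records, carried through to Day 361, and one row. Data collection does not change and no planned output is lost. The cost is slightly longer safety output.

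When the row is defined, the MAAE definition should be reconciled: Protocol 8.10.4 requires an unscheduled visit, while SAP 6.7.2 accepts an unscheduled or a scheduled one.
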